4.7 Immunogenicity Analysis

4.7.1 Background

Definition of baseline value

Baseline value is defined as the latest immunogenicity data collected prior to the first dose. If no immunogenicity data are collected prior to the first dose, baseline value is missing and will be imputed as anti-drug antibody negative for immunogenicity analyses.

Treatment-emergent anti-aducanumab antibody positive responses

Post-baseline positive anti-aducanumab antibody responses are defined as treatment-emergent if a subject is either (1) antibody negative at baseline; or (2) antibody positive at baseline but the post-baseline antibody response is more than 2-fold increase in titer compared to the baseline response.

Persistent and transient positive responses for the placebo-controlled period

Subjects with treatment-emergent positive anti-aducanumab antibody responses in the placebo-controlled period will be further classified as transient positive, if only a single positive evaluation occurs or more than 1 positive evaluation but occur with < 112 days (16 weeks) apart, or as persistent positive, if more than one consecutive positive evaluation occurs \ge 112 days (16 weeks) apart or a positive evaluation occurs at the last available time point with no further negative results available (including long-term extension).

4.7.2 Immunogenicity analysis

Immunogenicity population will be used to analyze immunogenicity data. Safety treatment groups will be used for immunogenicity analysis. Tables will be presented by treatment group (placebo, low dose, high dose and BIIB037 total; analysis display A in Appendix 6.1). Listings will be presented by treatment group stratified by ApoE status.

A summary table of subjects with treatment-emergent positive anti-aducanumab antibody responses results will be provided. The number and percentage of anti-aducanumab positive responses will be summarized at each visit and at any time post-baseline. Subjects with persistent response and subjects with transient response will be presented. A listing of subjects with anti-aducanumab antibody positive results will also be provided.

Visit windows for by visit summaries

For immunogenicity by visit summaries, the analysis visit should be defined using visit windows (see Table 11Table 7 below). If there is more than 1 value in the same analysis visit window for a subject, then the closest record to the target visit day will be used for the by visit analysis. If there are 2 values in the same analysis visit window with the same distance

Final V1.0

from the target visit day for a certain parameter for a subject, then the record with the later date will be used for the by visit analysis. If there are 2 values on the same day for a certain parameter for a subject, then the record with the later time will be used for the by visit analysis.

Table 11: Visit Windows for Immunogenicity by Visit Summaries

Analysis visit	Target visit day	Analysis visit window
Baseline	1	Most recent non-missing pre-dose value
Week 24	169	[2, 196]
Week 32	225	[197, 308]
Week 56	393	[393, 470]
Week 78	547	[470, the end day of the placebo-controlled period*]

^{*} The end day of the placebo-controlled period is the last day before the first infusion in LTE for subjects who enter LTE, and is the last day in study for subjects who do not enter LTE.

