3.7.2 Immunogenicity analysis

Immunogenicity population will be used to analyze immunogenicity data. LTE safety treatment groups will be used for immunogenicity analysis. Tables will be presented by LTE treatment group (late start low dose, late start high dose, early start low dose, early start high dose, and in addition late start total, early start total and BIIB037 total; analysis display A in Appendix 4.1). Listings will be presented by treatment group stratified by ApoE status.

A summary table of subjects with treatment-emergent positive anti-aducanumab antibody responses in the placebo-controlled and LTE active treatment period will be provided. The number and percentage of anti-aducanumab positive results will be summarized at each visit as well as at any time post-baseline in this period. Subjects with persistent response and

Final V1.0

subjects with transient response in this period will be presented. A listing of immunogenicity data in placebo-controlled and LTE period for subjects with anti-aducanumab antibody positive results will also be provided.

Visit windows for by visit summaries

For immunogenicity by visit summaries, the analysis visit should be defined using visit windows (see Table 7 below). If there is more than 1 value in the same analysis visit window for a subject, then the closest record to the target visit day will be used for the by visit analysis. If there are 2 values in the same analysis visit window with the same distance from the target visit day for a certain parameter for a subject, then the record with the later date will be used for the by visit analysis. If there are 2 values on the same day for a certain parameter for a subject, then the record with the later time will be used for the by visit analysis.

Table 7: Visit Windows for Immunogenicity by Visit Summaries

	Analysis visit window ¹			
	For subjects who received the	For subjects who received the		
	first dose of aducanumab in	first dose of aducanumab in		
Analysis visit	the placebo-controlled period	the LTE period		
Baseline	Last value prior to the first dose of	Last value prior to the first dose of		
	aducanumab	aducanumab		
Week 24	[2, 196]	[2, 252]		
Week 32	[197, 308]	NA		
Week 56	[309, 470]	[253, 420]		
Week 78	[471, end day of the placebo-	[421, 609]		
	controlled period ²]			
Week 80	[start day of the LTE period ³ , 644]	NA		
Week 104	[645, 812]	[610, 1260]		
Week 128	[813, 980]	NA		
Week 152	[981, 1169]	NA		
Week 182	[1170, 1820]	≥ 1261		

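### Immunogenicity windows in the placebo-controlled SAP (Table 11) leave days 309–392 in no visit, start Week 56 on its own target day and count day 470 twice, so early Week 56 samples drop out of the by-visit antibody summary

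*SAP*

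**What the plan says.** Section 4.7.2 of the placebo-controlled SAP assigns samples to visits by day: "For immunogenicity by visit summaries, the analysis visit should be defined using visit windows". The windows are in Table 11. Read as visit, target day and window, the post-baseline rows are:

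- The first row is "Week 24 169 [2, 196".
- The second row is "Week 32 225 [197, 308".
- The third row, the one at issue, is "Week 56 393 [393, 470".
- The fourth and last row is "Week 78 547 [470, the end day of the placebo-controlled period".

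The planned output is "The number and percentage of anti-aducanumab positive responses will be summarized at each visit and at any time post-baseline".

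Table 7 of the LTE SAP (section 3.7.2) covers the same placebo-controlled visits for subjects whose first aducanumab dose fell in that period. Its Week 24 and Week 32 windows equal those in Table 11. Its Week 56 row reads "Week 56 [309, 470] [253, 420"; the first bracket is for these early-start subjects and the second for subjects first dosed in the LTE. Week 78 for early-start subjects begins on day 471.

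**The concern.** The Week 56 window opens on its own target day, so it has no room for an early visit: a sample on day 393 counts and a sample on day 392 does not. The section offers no fallback. Its tie-break rules choose among several values inside one window; they cannot place a value that lies in no window, or choose between two windows for day 470. The nominal visit is not available either: the SAP uses it for serum concentrations (section 4.6.1) but not for immunogenicity.

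At stake is the Week 56 row of the by-visit antibody table, in all three arms. Two reports from one trial would also count the same early-start samples differently at Week 56.

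**Working it through.** **Inputs.** Target days 169, 225, 393 and 547, and the four post-baseline windows, from Table 11 of the placebo-controlled SAP. Week 56 as [309, 470] and Week 78 from day 471, from Table 7 of the LTE SAP (early-start column). Visit timing is not in the SAP, so the spreads in step 5 are assumptions.

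**1. Gap and overlap in Table 11 as printed.** Week 32 ends on day 308 and Week 56 starts on day 393. Unassigned days: 309 to 392, that is 392 − 309 + 1 = 84 days. Day 392 (one day early) maps to nothing, and so does day 309 (393 − 309 = 84 days early). Day 470 closes Week 56 and opens Week 78, so it maps to both.

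**2. Rebuilding the bounds.** Midpoints of adjacent target days:

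- (169 + 225)/2 = 197: the printed start of Week 32.
- (225 + 393)/2 = 309: follows directly on the printed end of Week 32 (308), but the printed start of Week 56 is 393.
- (393 + 547)/2 = 470: the printed start of Week 78.

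Only the Week 56 start departs from the pattern, and it repeats the number in the target-day column beside it.

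**3. Comparison with the SAP's other tables.** Tables 3 (efficacy), 7 (laboratory) and 10 (vital signs) are contiguous: each window starts one day after the previous one ends. In each, the midpoint day opens the later window, for example (183 + 351)/2 = 267 and (351 + 547)/2 = 449 in Table 3, and (169 + 337)/2 = 253 in Table 7.

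**4. Effect of correction.** With Week 56 = [309, 470] and Week 78 from 471, every day from 2 onward falls in exactly one window. The same is true with Week 56 = [309, 469] and Week 78 from 470.

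**5. Share of Week 56 samples lost, under assumed timing.**

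*Uniform over whole days within ±k of day 393:* share drawn before day 393 = k/(2k + 1).

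| k (days) | Share lost |
|---|---|
| 3 | 3/7 = 43% |
| 7 | 7/15 = 47% |
| 14 | 14/29 = 48% |

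*Normal with mean delay m and standard deviation s, with a half-day correction:* share = Φ((−0.5 − m)/s). For m > 0 this falls as m rises and rises with s, so the extremes over m = 3 to 14 and s = 5 to 10 lie at two corners.

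| m (days) | s (days) | Share lost |
|---|---|---|
| 14 | 5 | Φ(−2.90) = 0.2% |
| 3 | 5 | Φ(−0.70) = 24% |
| 14 | 10 | Φ(−1.45) = 7% |
| 3 | 10 | Φ(−0.35) = 36% |

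**The case against.** **The output is narrow.** The by-visit table is descriptive, with no test or decision rule attached. The tertiary endpoint is the incidence of anti-aducanumab antibodies, which the any-time summary serves. That summary, the persistent/transient classification (section 4.7.1, based on time between evaluations) and the listing of positive subjects do not use the windows. All of this stands and limits the point to one row of one table.

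**Gaps can be deliberate.** Table 4 (amyloid PET) has none of its windows covering days 267–448. There, however, the SAP gives a reason: the Week 26 and Week 78 windows are taken over from efficacy, and no PET visit is scheduled between them. No reason is given in Table 11, and its gap runs right up to a scheduled visit's target day.

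**The loss may be small.** If visits run two weeks late with little spread, almost nothing is lost. This also stands: only the 84-day gap is a documented figure, and any percentage depends on assumed timing.

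**Day 470 hardly matters.** It lies 77 days from either target (470 − 393 = 547 − 470 = 77), so few samples, if any, will fall there. It needs tidying but carries no weight.

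**Two stronger readings a reader might infer.** The first is that the Week 56 positivity percentage is wrong. The documents do not show this: numerator and denominator both shrink, and the percentage is biased only if the timing of the draw relates to antibody status. The second is that the two SAPs conflict for every subject. They do not: the LTE window [309, 470] applies to subjects first dosed with aducanumab in the placebo-controlled period. Subjects randomised to placebo have LTE windows counted from their first aducanumab dose, so they have no competing placebo-period Week 56 window.

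**Conclusion.** Table 11 is wrong as written. It leaves 84 days unassigned, gives Week 56 no allowance for early visits and assigns one day twice. That this is a slip and not a choice is supported by the midpoint pattern, the contiguous Tables 3, 7 and 10, and the LTE SAP's own window.

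The size of the consequence is uncertain. Between about 0.2% and 48% of Week 56 samples would be missing from the by-visit summary across the assumed timings, with the top of the range requiring visits symmetric around day 393. What is shown is a loss of records and precision at one visit, plus a disagreement with the LTE report for early-start subjects. No efficacy result depends on it. It should be corrected because the rule, applied literally, discards valid samples.

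**What to change.** In Table 11, start Week 56 at day 309 and place day 470 in one window only, in the same way in both SAPs. Two versions work:

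- Week 56 [309, 470] with Week 78 from day 471. This matches Table 7 of the LTE SAP and leaves that plan unchanged.
- Week 56 [309, 469] with Week 78 from day 470. This follows the convention of the other tables in the placebo-controlled SAP, where the midpoint day goes to the later visit, but Table 7 of the LTE SAP must then change too.

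Either removes the gap and the overlap. The cost is one table correction in the placebo-controlled SAP, a second in the LTE SAP if the latter version is chosen, and the matching change in the analysis programs. No new data are needed.

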4.8 Additional Exploratory Endpoints

5 INTERIM ANALYSIS

An interim analysis will occur after approximately 50% of the subjects have had the opportunity to complete the Week 78 visit for both 221AD301 and 221AD302. To maintain the integrity of the study in the event of the interim analysis, an independent group external to Biogen that will not be involved in the conduct of the study after unblinding will perform the interim analysis. The IDMC will review the unblinded results of the interim analysis provided by the independent group and will make a recommendation to Biogen based on pre-specified criteria.

An interim analysis for futility of the primary endpoint will be performed to allow early termination of the studies if it is evident that the efficacy of aducanumab is unlikely to be achieved. The futility criteria will be based on conditional power, which is the chance that the primary efficacy endpoint analysis will be statistically significant in favor of aducanumab at the planned final analysis, given the data at the interim analysis. The conditional power is calculated assuming that the future unobserved effect is equal to the maximum likelihood estimate of what is observed in the interim data:

Final V1.0

$$CP(Z(1) \ge Z_{\alpha} | Z(t)) = 1 - \phi \left(\frac{Z_{\alpha} \sqrt{n_2} - Z(t) \sqrt{n_1}}{\sqrt{n_2 - n_1}} - \frac{Z(t) \sqrt{n_2 - n_1}}{\sqrt{n_1}} \right)$$

where t is the fraction of information and Z(t) is the observed Z-statistic at the interim analysis, Z(1) is the Z-statistic and α is the type I error at the final analysis, n_1 and n_2 are the number of subjects at the interim and at the final analysis, respectively.

The futility decision will primarily be based on the conditional power for the primary efficacy endpoint. The study will not be considered as futile unless both studies 221AD301 and 221AD302 have conditional power for the primary efficacy endpoint less than 20% in both the high-dose and low-dose treatment groups. Given the insufficient knowledge of aducanumab's potential effects on various functional/cognition endpoints or in certain subgroups at the present time, other data in addition to the pre-specified futility criteria will be considered as well, and the IDMC may recommend the studies to be continued as planned based on the weight of the evidence.

An interim analysis for superiority may be performed, to allow the possibility to demonstrate the treatment effect early. If an interim analysis for superiority is performed, the O'Brien-Fleming stopping boundary will be used. If an interim analysis for superiority is not performed, then no alpha adjustment will be used for the final analysis after all subjects have had the chance to complete the Week 78 visit.

Final V1.0

6 APPENDIX

6.1 Analysis Display

Analysis display A

Placebo BIIB037 low dose BIIB037 high dose

Analysis display B

	Placebo		BIIB	037 low dose		BIII	B037 high dos	e
ApoE e4+	ApoE e4-		ApoE e4+	ApoE e4-		ApoE e4+	ApoE e4-	
placebo	placebo	Total	3 mg/kg	6 mg/kg	Total	10 mg/kg	10 mg/kg	Total

6.2 Protocol Deviation Classification

Deviation Category	Deviation Description	Severity Classification
Administrative criteria	Study team member performing study assessments without being authorized as per delegation log.	Minor
Administrative criteria	Unblinded information made available to the blinded CRA.	Major
Administrative criteria	Unblinded information made available to the blinded site personnel.	Major
Administrative criteria	Incorrect version of any assessments used	case by case
Administrative criteria	Filing issues misfiling of documents	N/A
Administrative criteria	Correction of source data not compliant with GCP	N/A
Administrative criteria	Sharing of account credentials between raters on the MedAvante Virgil tablet/Portal, or sharing of accounts on any study system	Major
Concomitant Medications	Administration of any vaccination/booster should be given < 10 days prior to any dosing visit or 10 days after a dosing visit.	Minor
Concomitant Medications	Administration of any disallowed concomitant therapy to the subject.	Major
Concomitant Medications	Change of medications that subjects were receiving at enrollment or start of new medications or herbal preparations during the study period, without consultation with the investigator and review with the Medical Monitor	Case by case basis
Concomitant Medications	Change in AD medications during course of the study.	Minor
Eligibility and Entry criteria	Any "no" response to inclusion criteria and/or any "yes" response to exclusion criteria and subject was subsequently randomized for criteria.	Major
Eligibility and Entry criteria	Any eligibility assessment not performed.	Major
Eligibility and Entry criteria	Any eligibility assessment performed after the randomization of the patient (including lab samples), and subject is ineligible based upon assessment.	Major
Eligibility and Entry Criteria	Exclusionary lab value results but subject was dosed.	Major
Eligibility and Entry criteria	Subject not eligible based on scores of CDR, MMSE, RBANS DMI, as defined by inclusion criterion #6.	Major
Eligibility and Entry criteria	Subject on allowed chronic medications that have not been stable for at least 4 weeks prior to Screening V1 or use of AD medications at doses that have not been stable for at least 8 weeks prior to Screening V1.	Major

Informed Consent	Subject/informant/legally authorized representative did not sign Main ICF, PET ICF, and/or Substudy ICFs (and substudy procedures were conducted). Not clear on the ICF who has been signing the document (patient or legal representative).	Major
Informed Consent	Principal Investigator / individual obtaining consent did not sign Main ICF, PET ICF, and/or Substudy ICFs (and substudy procedures were conducted).	Major
Informed Consent	Not clear on the the ICF who has been signing the document (patient or legally authorized representative).	Major
Informed Consent	ICF signed by either only patient or only care giver/legally authorized representative, when ICF should have been signed by both.	Major
Informed Consent	Incorrect or outdated version of Main ICF, PET ICF, and/or Substudy ICFs signed by subject/informant/legally authorized representative.	Major
Informed Consent	IEC/IRB contact details or site's contact details not included on ICF.	Minor
Informed Consent	Incorrect completion of ICF (i.e., subject/study partner/LAR/person obtaining consent did not provide date of signature; subject/study partner/LAR/person obtaining consent noted incorrect date of signature; subject/study partner/LAR/person obtaining consent printed name when should have signed, subject/study partner/LAR/person obtaining consent signed on line for printed name, printed name on line for signature, etc.)	Minor
Informed Consent	Site personnel who signed ICF is not on Site Personnel Signature Delegation Log and/or not authorized by PI to sign ICF	Major
Informed Consent	No evidence (source documentation) that Informed Consent was obtained from the study subject / study partner.	Major
Informed Consent	ICF obtained by subject is not in subject's native language.	Major
Informed Consent	Protocol specific procedures such as physical exam, medical history, neurological history, ECGs, rater scales, lab tests, blood draws, including first study drug dose performed prior to the date of the consent.	Major
Informed Consent	Subject and/or Study Partner/Caregiver not signing ICFs at time of reconsent.	Major
Informed Consent	Untimely reconsenting of subject/caregiver on newly approved ICFs.	Major
Investigational Product Compliance	IP storage temperature out of range and site used IP without confirmation from Biogen regarding usability	Case by case basis
Investigational Product Compliance	Incorrect cohort IP dispensed to subject	Major
Investigational Product Compliance	IP is not stored in blinded manner.	Major
Investigational Product Compliance	Unblinded pharmacist discarded/destroyed used IP vial prior to IP accountability being conducted by unblinded CRA and without previous approval.	case by case basis
Investigational Product Compliance	IP temperature log is not being maintained nor checked by the unblinded pharmacist.	Major
Investigational Product Compliance	Non-compliant with IP usage according to DHA (note: this does not include deviation regarding removing overfill on saline bag)	Major
Investigational Product Compliance	Dosing based on weight calculation is inaccurate (i.e., discrepancies between Weight Communication Form and IXRS entry, ratio not respected when preparing dose, etc.)	Major
Investigational Product Compliance	Overdose of IP occurs.	Major
Investigational Product Compliance	Overdose Form not faxed to Quintiles Lifecycle Safety within 24 hours of site being made aware of an overdose.	Major
Investigational Product Compliance	Titration schedule not respected when dosing subject.	Major
Investigational Product Compliance	Down-dosing / discontinuation of dosing not respected by the unblinded pharmacist following ARIA-H and ARIA-E cases, as prescribed by the protocol, investigator, Medical Monitor, and/or sponsor.	Major

Investigational Product Compliance	, , ,				
Investigational Product Compliance	IP storage temperature out of range (2-8 °C).				
Investigational Product Compliance	Administration of expired IP.				
Investigational Product Compliance	IP rounding discrepancies not in accordance with the Directions for Handling & Administration document (DHA).				
Investigational Product Compliance	Administration of IP that was rejected after a temperature excursion.	Major			
Investigational Product Compliance	IP administered in less than 21 days.	Minor			
Laboratory assessments criteria	Ambient samples received at central laboratory that should have been shipped frozen.	Minor			
Laboratory assessments criteria	Frozen samples received at central laboratory that should have been shipped ambient.	Minor			
Laboratory assessments criteria	Lab samples not drawn, or results unavailable.	Minor			
Laboratory assessments criteria	Laboratory results not acknowledged by PI, or medically qualified and delegated study personnel.	case by case			
Laboratory assessments criteria	Pre-dose and/or post-dose PK samples not collected, or not collected within protocol specified time.	Minor			
Laboratory assessments criteria		Minor			
Laboratory assessments criteria	Lab specimens temperature log is not being maintained nor checked by applicable study personnel.				
Laboratory assessments criteria	Use of incorrect lab kit.				
Laboratory assessments criteria	PBMC not collected, or not collected within protocol specified time.				
Other	Site repeatedly commits same minor deviations.				
Randomization criteria	Subject recorded as randomized in IXRS by mistake but not dosed.	Major			
Randomization criteria	Subject randomized to wrong arm due to mis-entry of ApoE ε4 carrier status.				
Regulatory or Ethics Approval Criteria	No evidence that IRB / CEC / LEC approved the final protocol.	Major			
Regulatory or Ethics Approval Criteria	No evidence that IRB / CEC / LEC was notified of protocol amendments in a timely manner.	Minor			
Regulatory or Ethics Approval Criteria	Failure to notify or obtain approval from the IRB / CEC / LEC of a change of investigator.	Minor			
Regulatory or Ethics Approval Criteria	Failure to obtain or keep updated regulatory authorization to conduct a study.	Major			
Regulatory or Ethics Approval Criteria	Failure to obtain IRB / CEC / LEC approval of a subject directed document (e.g., subject questionnaires, advertisements, etc.)	Major			
Regulatory or Ethics Approval Criteria	Failure in Safety Reporting as per local requirements (SUSARS, line listings, progress reports, etc.)				
Serious Adverse Event Criteria	SAEs not appropriately reported (i.e., reported as an AE when SAE criteria have been met, or SAE not reported within 24 hours).				
Serious Adverse Event Criteria	Pregnancies not appropriately reported within 24 hours of study site staff becoming aware of the pregnancy.				
Serious Adverse Event Criteria	Adverse Events of Special Interest not reported within 72 hours following the receipt of abnormal MRI findings from the central MRI reader.				
erious Adverse Event Criteria SAEs not appropriately reported to the IRB/EC.					
Study Procedures criteria	Inconsistent rater used for primary, secondary endpoints	Major			

Study Procedures criteria	CDR raters were performing other assessments on subjects they performed CDRs for.	Major			
Study Procedures criteria	Secondary endpoint assessments raters were performing other assessments on subjects they performed these assessments for.	Major			
Study Procedures criteria	MOCA was administered by a rater rather than the treating HCP.	Major			
Study Procedures criteria	Assessment performed by non-qualified rater				
Study Procedures criteria	Any eligibility criteria not confirmed prior to dosing, but deemed eligible post- randomization (including verification of eligibility based on cancer criteria with Medical Monitor [inclusion criterion #10]).	Minor			
Study Procedures criteria	MRI and/or PET scan being conducted as part of Screening Visit 2 or Screening Visit 3 procedures without PI verification of eligibility at Screening Visit 1 (including laboratory and cognitive assessment eligibility) without permission of the sponsor/Medical Monitor. Please note that ApoE £4 results are not necessary to move onto Screening Visits 2 or 3.				
Study Procedures criteria	PET scan being conducted as part of Screening Visit 3 prior to MRI central read confirming eligibility at Screening Visit 2, without permission of the sponsor/Medical Monitor.	Minor			
Study Procedures criteria	Dose reduction administered by PI/sub-I when protocol requires return to last dose following temporary discontinuation of IP following ARIA event under Protocol v. 3.	case by case			
Study Procedures criteria		Minor			
Study Procedures criteria	Primary endpoint assessment not conducted or administered at a study visit, as per protocol. Please note that deviation will not apply for any cognitive assessments that were not administered or completed, due to subject's decline in cognition.				
Study Procedures criteria	Secondary endpoint assessments not conducted or administered at a study visit, as per protocol. Please note that deviation will not apply for any cognitive assessments that were not administered or completed, due to subject's decline in cognition.				
Study Procedures criteria	Tertiary endpoint efficacy assessments not conducted or administered at a study visit, as per protocol. Please note that deviation will not apply for any cognitive assessments that were not administered or completed, due to subject's decline in cognition.				
Study Procedures criteria	C-SSRS not conducted or administered at a study visit, as per protocol.	Minor			
Study Procedures criteria	Systolic blood pressure, diastolic blood pressure, heart rate, body temperature, and/or respiratory rate not assessed as part of vital signs, or vital signs not measured with the subject supine and/or after the subject has been resting for at least 10 minutes.				
Study Procedures criteria	Serum pregnancy test not conducted at Screening Visit 1, or urine pregnancy test not conducted at applicable study visits for subjects of child-bearing potential.				
Study Procedures criteria	MRI and/or PET scan being conducted on subsequent subjects should site not receive passing QC report on first in-vivo scan.				
Study Procedures criteria	ARIA management not being followed as per protocol specifications.	Major			
Study Procedures criteria	Non-IEC/IRB approved document(s) dispensed to subject	Major			
Study Procedures criteria	Unscheduled visit not conducted due to AD medication change, or conducted after AD medication change occurred.				
Study Procedures criteria	Study MRIs not conducted within study visit schedule.				
Study Procedures criteria	Study MRIs missed				
Study Procedures criteria	Administration of rating scales over the telephone.	Minor			
Study Procedures criteria	Missed MOCA at an Unscheduled MRI visit.	Major			
Study Procedures criteria	Missed MOCA at Day 1 Visit.	Minor			
tudy Procedures criteria Missed physical exam, neurological exam, or ECG at study visit.					

Final V1.0

Study Procedures criteria	Missed PET scan at timepoints for PET substudy subjects.		
Study Procedures criteria	Ligand dose administration error Major		
Study Procedures criteria	Infusion conducted prior to receipt and review of MRI central read results	Case by case	
Visit Schedule Criteria	Study visit or procedures conducted out of window. Please note special attention to the ADCS-ADL-MCI, ADAS-Cog, and NPI at Screening Visit 2 being conducted within 14 days of Screening Visit 1.		
Visit Schedule Criteria	Occurrence of randomization outside of 60-day screening window without sponsor approval.	Minor	
Visit Schedule Criteria	Occurrence of randomization outside of 90 days.	Major	

